## 6.7 Intervention After the End of the Study

There is no study-specified intervention following the end of the study.

## 6.8 Clinical Supplies Disclosure

This study is open-label; therefore, the participant, the study site personnel, the Sponsor, and/or designee are not blinded. Study intervention, MK-8353 50 mg (or 100 mg) or selumetinib 25 mg, are included in the label text; random code/disclosure envelopes or lists are not provided.

## 6.9 Standard Policies

This section is not applicable.

## 7 DISCONTINUATION OF STUDY INTERVENTION AND PARTICIPANT WITHDRAWAL

### 7.1 Discontinuation of Study Intervention

Discontinuation of study intervention does not represent withdrawal from the study.

As certain data on clinical events beyond study intervention discontinuation may be important to the study, they must be collected through the participant's last scheduled follow-up, even if the participant has discontinued study intervention. Therefore, all participants who discontinue study intervention prior to completion of the protocol-specified treatment period will still continue to participate in the study as specified in Section 1.3 and Section 8.11.3.

Participants may discontinue study intervention at any time for any reason or be discontinued from the study intervention at the discretion of the investigator should any untoward effect occur. In addition, a participant may be discontinued from study intervention by the investigator or the Sponsor if study intervention is inappropriate, the study plan is violated, or for administrative and/or other safety reasons. Specific details regarding procedures to be performed at study intervention discontinuation are provided in Section 8.1.9.

A participant must be discontinued from study intervention but continue to be monitored in the study for any of the following reasons:

- The participant or participant's legally acceptable representative requests to discontinue study intervention.
- The participant interrupts study intervention administration due to treatment-related toxicity for more than 14 consecutive days in cycle 1 or has >25% cumulative missed doses.
- The participant has a medical condition or personal circumstance which, in the opinion of the investigator and/or Sponsor, placed the participant at unnecessary risk from continued administration of study intervention.
- The participant has a confirmed positive serum pregnancy test.
- Confirmed radiographic disease progression outlined in Section 8.2 (exception if the Sponsor approves treatment continuation).
- Unacceptable adverse experiences as described in Section 8.4.
- Progression or recurrence of any malignancy, or any occurrence of another malignancy that requires active treatment.

- Intercurrent illness other than another malignancy as noted above that prevents further administration of treatment.
- Investigator's decision to discontinue treatment.

For participants who are discontinued from study intervention but continue to be monitored in the study, all visits and procedures, as outlined in the SoA, should be completed.

Discontinuation from study intervention is "permanent." Once a participant is discontinued, he/she shall not be allowed to restart study intervention.

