Participants may have up to 2 dose modifications of MK-8353 and selumetinib throughout the course of the study, as described in [Table 7](#). If further toxicity occurs or the criteria for resuming treatment are not met, the participant must be discontinued from the study treatment. If a participant experiences several toxicities and there are conflicting recommendations, follow the most conservative dose adjustment recommended (dose reduction appropriate to the most severe toxicity).

Exceptional circumstances to following the dose modification tables below may be considered after consultation with the Sponsor.

Table 7 MK-8353 and Selumetinib Dose Modification and Treatment Discontinuation Guidelines for Drug-Related Adverse Events

Eye disorders – Retinal Events (including serous detachment of the retina)	
Grade 1	Maintain dose level of MK-8353 and selumetinib and repeat ophthalmic monitoring including visual acuity assessment and ocular coherence tomography (OCT) within 10 days.
Grade 2	Interrupt MK-8353 and selumetinib dosing and refer the participant to ophthalmologist within 1 week and obtain OCT within 10 days: If resolved to baseline or Grade $\leq 1$ within 10 days, resume treatment at current dose level and continue schedule of visual assessments established per protocol. If not resolved to baseline or Grade $\leq 1$ within 10 days, resume treatment at reduced dose level and continue the schedule of events of visual assessments established per protocol.
Grade 3	Interrupt MK-8353 and selumetinib and refer the participant to ophthalmologist within 1 week and obtain OCT: If resolved to baseline or Grade $\leq 1$ within 7 days, resume treatment at a reduced dose level and continue schedule of visual assessments established per protocol. If not resolved to baseline or Grade $\leq 1$ within 7 days, continue to hold the MK-8353 and selumetinib dose and repeat ophthalmic assessment in 10 days. If resolved to baseline or Grade $\leq 1$ , resume treatment at reduced dose level and continue schedule of visual assessments established per protocol. If remains Grade 3, permanently discontinue MK-8353 and selumetinib.
Grade 4	Permanently discontinue MK-8353 and selumetinib and immediately follow up with ophthalmic monitoring.
Eye disorder – Retinal Vein Occlusion (RVO)	
Any Grade	Permanently discontinue MK-8353 and selumetinib.
Other Eye Disorders (ie, Non-retinal Events)	

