Grade 1-2	Maintain dose level of MK-8353 and selumetinib and increase frequency of ophthalmic monitoring to at least 14 days until stabilization or resolution.
Grade 3	Interrupt MK-8353 and selumetinib and refer participant to ophthalmologist within 1 week: If resolved to Grade $\leq 1$ in $\leq 21$ days, reduce 1 dose level of MK-8353 and selumetinib. If not resolved to Grade $\leq 1$ in $\leq 21$ days, permanently discontinue MK-8353 and selumetinib.
Grade 4	Permanently discontinue MK-8353 and selumetinib.

Liver-related Adverse Events	
Grade 1 AST or ALT (> ULN - 3 × ULN)	Maintain dose level of MK-8353 and selumetinib.
Grade 2 AST or ALT (>3 - 5.0 × ULN) or 3 × baseline value (if liver metastasis) AND blood bilirubin ≤2.0 × ULN	Interrupt dose of MK-8353 and selumetinib until resolved to Grade ≤1 (or Grade ≤2 in case of liver metastasis), then: 
 
• If resolved in ≤14 days, maintain dose level of MK-8353 and selumetinib.
 
• If resolved in >14 days, reduce dose level of MK-8353 and selumetinib.
 
 Recurrence: 
 
• Interrupt dosing of MK-8353 and selumetinib until resolved to Grade ≤1 (or Grade ≤2 in case of liver metastasis), then resume treatment at a reduced dose.
 

Grade 2 AST or ALT (> 3 - 5.0 × ULN) or 3 × baseline value (if liver metastasis) AND blood bilirubin > 2.0 × ULN	Interrupt dose of MK-8353 and selumetinib until resolved to Grade ≤1 (or Grade ≤2 in case of liver metastasis), then: 
 
• If resolved in ≤7 days, resume treatment at a reduced dose of MK-8353 and selumetinib.
 
• If not resolved in ≤7 days, permanently discontinue MK-8353 and selumetinib.
 

Grade 3 AST or ALT (>5.0 - 8.0 × ULN) AND blood bilirubin ≤2.0 × ULN	Interrupt dose of MK-8353 and selumetinib until resolved to Grade ≤1 (or Grade ≤2 in case of liver metastasis), then: 
 
• If resolved in ≤14 days, maintain dose level of MK-8353 and selumetinib.
 
• If resolved in >14 days, reduce dose level of MK-8353 and selumetinib.
 
 Recurrence: 
 
• Interrupt dosing of MK-8353 and selumetinib until resolved to Grade ≤1 (or Grade ≤2 in case of liver metastasis), then resume treatment at a reduced dose.
 

AST or ALT (>8 x ULN) AND blood bilirubin* ≤ 2.0 × ULN	Permanently discontinue MK-8353 and selumetinib.

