AST or ALT (>5.0 × ULN) AND blood bilirubin* >2.0 × ULN	Permanently discontinue MK-8353 and selumetinib.
AST or ALT Grade 4 (>20.0 × ULN)	Permanently discontinue MK-8353 and selumetinib.

Cardiac Disorders	
Left ventricular systolic dysfunction Asymptomatic decrease of >10% in LVEF compared to baseline and the LVEF is below the institution's lower limit of normal	
Interrupt dose of MK-8353 and selumetinib and repeat evaluation of LVEF within 2 weeks.
 
 
If the LVEF recovers (defined as LVEF <math>\geq 50\%</math> or <math>\geq</math>LLN and absolute decrease <math>\leq 10\%</math> compared to baseline) <math>\leq 3</math> weeks, reduce 1 dose level after approval of the Sponsor Medical Monitor. Monitor LVEF 2 weeks after restarting on MK-8353 and selumetinib, every 4 weeks for 12 weeks and subsequently as per protocol.
 
If the LVEF does not recover within 3 weeks, permanently discontinue participant from study treatment. Closely monitor LVEF until resolution (or 16 weeks).
 

Grade 3-4	Permanently discontinue participant from MK-8353 and selumetinib. Closely monitor LVEF until resolution (or 16 weeks).
CK Elevation	
Grade 1-2	
Continue treatment on same dose level. Ensure patient is adequately hydrated. Monitor closely CK and serum creatinine levels.                      (If total CK <math>\geq 3 \times</math> ULN, measure isoenzymes and myoglobin in blood and urine).

Grade 3 (>5.0 - 10.0 $\times$ ULN) without renal impairment (ie, serum creatinine $< 1.5 \times$ ULN or $1.5 \times$ baseline)	
If asymptomatic, maintain dose of MK-8353 and selumetinib. Monitor closely and measure isoenzymes and myoglobin in blood and urine.
 
If symptomatic (muscle pain/spasms or muscle weakness), interrupt dose of MK-8353 and selumetinib until resolved to CTCAE Grade <math>\leq 1</math> and monitor closely, then:
 
 
If resolved in <math>\leq 21</math> days, reduce 1 dose level of MK-8353 and selumetinib.
 
If resolved in <math>> 21</math> days, permanently discontinue MK-8353 and selumetinib.
 

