Grade 3	First occurrence: Treatment with MK-8353 and selumetinib should be interrupted. Reassess the participant weekly. Consider referral to dermatologist and manage rash per dermatologist's recommendation. Interrupt treatment until improvement to Grade $\leq 1$ . Resume treatment with MK-8353 and selumetinib at a reduced dose level.  Second occurrence: Interrupt treatment until improvement to Grade $\leq 1$ . Resume treatment with MK-8353 and selumetinib at a reduced dose level. If participant is at the lowest dose, participant should be discontinued. Consider referral to dermatologist and manage rash per dermatologist's recommendation.
Grade 4	Permanently discontinue MK-8353 and selumetinib.
Diarrhea	
Uncomplicated Grade 1-2	Consider temporary interruption of MK-8353 and selumetinib until resolved to Grade $\leq 1$ . Treatment with MK-8353 and selumetinib may then be resumed at the same dose level.
Complicated Grade 1-2	Temporarily interrupt MK-8353 and selumetinib treatment until resolved to Grade $\leq 1$ . Restart MK-8353 and selumetinib at one reduced dose level. If participant is at the lowest dose, participant should be discontinued.
Grade 3-4	Temporarily interrupt MK-8353 and selumetinib treatment until resolved to Grade $\leq 1$ . Restart MK-8353 and selumetinib at a reduced dose level. If participant is at the lowest dose, participant should be discontinued.
Nausea/Vomiting	
Grade 1-2	Treatment with MK-8353 and selumetinib should be maintained at the current dose. Promptly institute antiemetic measure.
Grade 3	Temporarily interrupt MK-8353 and selumetinib treatment until resolved to Grade $\leq 1$ . Resume treatment with MK-8353 and selumetinib at the same dose if, in the judgment of the investigator, the toxicity is considered to be unrelated to selumetinib, or at one reduced dose level.  Note: Interrupt dose for $\geq$ Grade 3 vomiting or Grade 3 nausea only if the vomiting or nausea cannot be controlled with optimal antiemetics (as per local practice).
Grade 4	Permanently discontinue MK-8353 and selumetinib treatment

Interstitial Lung Disease/Pneumonitis	
Grade 1	Maintain dose level of MK-8353 and selumetinib. Monitor weekly.
Grade 2	Withhold MK-8353 and selumetinib for up to 3 weeks. 
 
• If improved to Grade 0 or 1, resume treatment at 1 reduced dose level of MK-8353 and selumetinib
 
• If not resolved within 3 weeks, permanently discontinue MK-8353 and selumetinib.
 

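### Section 7.1 makes a treatment-related hold of more than 14 days in Cycle 1 a permanent stop, Table 7 directs resumption after such holds, and nothing says which prevails

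*Combined protocol and SAP*

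**What the plan says.** Section 7.1 lists reasons for which a participant must stop study intervention. One is interruption due to treatment-related toxicity "for more than 14 consecutive days in cycle 1 or has >25% cumulative missed doses". The stop is final: "Once a participant is discontinued, he/she shall not be allowed to restart study intervention".

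Section 6.6.4.1 also uses mandatory language: the doses of both drugs must be modified according to Table 7. No row of Table 7 is confined to Cycle 2 onward. Several rows provide for resumption after long holds:

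- AST/ALT Grade 2 or Grade 3 with bilirubin at or below 2 times ULN: if resolution takes more than "14 days, reduce dose level of MK-8353 and selumetinib".
- Retinal Grade 3 not resolved within 7 days: "continue to hold the MK-8353 and selumetinib dose and repeat ophthalmic assessment in 10 days", then resume at a reduced dose if resolved.
- LVEF decrease: resume at a reduced dose if recovered within 3 weeks. The stop comes only later: "If the LVEF does not recover within 3 weeks, permanently discontinue participant from study treatment".
- Grade 2 pneumonitis: "Withhold MK-8353 and selumetinib for up to 3 weeks", then resume reduced if improved. Uncomplicated DVT/PE has the same window.
- Complicated or Grade 3-4 diarrhea, and Grade 3 nausea/vomiting: "Temporarily interrupt MK-8353 and selumetinib treatment until resolved to Grade" 1 or lower, with no time limit.

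Two other places use a 25% threshold, and both name Cycle 1: DLT criterion 9 in Section 6.6.2 (more than 25% of doses missed because of drug-related AEs) and the evaluability rule in Section 5.6 (less than 75% received). Section 5.6 also lets a participant with a Cycle 1 DLT continue if deriving clinical benefit, after Sponsor-investigator discussion.

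**The concern.** For one participant with one toxicity, the protocol gives two mandatory instructions that cannot both be followed. Someone whose ALT elevation takes 16 days to resolve in Cycle 1 must stop permanently under Section 7.1 and must resume at a reduced dose under Table 7. One error re-exposes a participant whom Section 7.1 removes; the other ends treatment that Table 7 allows. Study drug discontinuations due to an AE are a listed primary endpoint (Section 3), so that count would depend on which section was applied.

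The second limb of the Section 7.1 rule adds a smaller problem. Without a period, the 25% limit could mean 25% of Cycle 1 doses or 25% of all doses scheduled to date, and the two readings can give opposite answers for the same short hold.

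**Working it through.** **1. Scheduled doses.** Both drugs are given BID, 4 days on and 3 days off (Table 4), in 3-week cycles. Dosing days in a cycle are 1-4, 8-11 and 15-18, which is 12 days × 2 = 24 doses per drug. Check against Section 4.3.2: 250 mg × 24 = 6000 mg and 125 mg × 24 = 3000 mg. Both stated cycle totals are reproduced. The 25% threshold is 0.25 × 24 = 6 doses, so more than 25% means at least 7.

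**2. Sorting the Table 7 rows that interrupt and then resume.**

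| Relation to the 14-day limit | Rows | Count |
|---|---|---|
| Directs resumption after, or within a window longer than, 14 days | AST/ALT Grade 2 and Grade 3 (bilirubin ≤2 × ULN); retinal Grade 3 (7 + 10 = 17 days); non-retinal eye Grade 3; LVEF decrease; CK Grade 3 symptomatic; CK Grade 4 asymptomatic; CK Grade 3-4 with renal impairment; ILD Grade 2; uncomplicated DVT/PE | 10 |
| Only permits restart (21 days, investigator discretion) | Other Grade 3 | 1 |
| Silent on duration | Rash Grade 2; rash Grade 3; three diarrhea rows; nausea/vomiting Grade 3 | 6 |
| Within 14 days | Retinal Grade 2 (10 days); AST/ALT Grade 2 with bilirubin >2 × ULN (7 days) | 2 |

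10 + 1 + 6 + 2 = 19. The row for other Grade 1-2 events has no resume rule and is left out. The only outer bound on the silent rows is the 12-week noncompliance rule in Section 6.4.

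**3. Doses missed by holds lying wholly inside Days 1-21** (calendar days, scheduled off-days included).

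| Hold length | Start days | Doses missed of 24 | Share |
|---|---|---|---|
| 3 days | 1-19 | 0-6 | 0-25% |
| 4 days on a full dosing block | 1, 8 or 15 | 8 | 33% |
| 7 days | 1-15 | 8 | 33% |
| 10 days | 1-12 | 8-14 | 33-58% |
| 14 days | 1-8 | 16 | 67% |
| 15 days | 1-7 | 16-18 | 67-75% |
| 21 days | 1 | 24 | 100% |

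**4. The 14-day limb.** A hold with more than 14 days inside Cycle 1 must start by Day 7 and misses 16 to 24 of 24 doses (67-100%). If the cause is treatment-related, it already meets DLT criterion 9. A 15-day hold starting on Day 8 has only Days 8-21, exactly 14 days, in the cycle. Whether Section 7.1 catches it depends on whether later days count, which the text does not say.

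**5. The 25% limb under two readings.** On Cycle 1 doses, one missed 4-day block is 8/24 = 33% and a mandatory stop. That defeats the same-dose resumptions in Table 7 (retinal Grade 2 within 10 days; the two AST/ALT rows within 14 days). It also makes the 14-day limb redundant, since every such hold misses at least 67%. On doses scheduled to date, the same 8 doses are 8/48 = 16.7% by the end of Cycle 2 and 8/72 = 11.1% by the end of Cycle 3, with no stop.

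**The case against.** The best defence is that Section 7.1 is a specific Cycle 1 limit and Table 7 a general set of guidelines, so the specific rule caps the general one. Table 7 is titled as guidelines, and Section 6.6.4.1 adds: "Exceptional circumstances to following the dose modification tables below may be considered after consultation with the Sponsor". That is a sensible reading, and the fix adopts it. But the exception covers departures from the dose modification tables and does not mention Section 7.1. The nearby rule to take the most conservative adjustment covers several toxicities in one participant, not two sections. Section 7.1 writes a Sponsor exception into its progression criterion and none into this one. The precedence remains an inference.

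It can also be said that sites do not decide alone: a drug-related hold this long is a DLT, and Section 5.6 sends continuation after a DLT through Sponsor-investigator discussion. That stands, and it reduces divergence between sites, but it does not tell the Sponsor which rule applies.

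On the 25% limb, the contrast between consecutive and cumulative misses makes Cycle 1 a natural reading, supported by criterion 9 and Section 5.6. The Pharmacy Manual, which is not available here, is said to cover missed doses. This part is therefore a missing definition.

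A reader might infer that 17 of the 19 rows contradict Section 7.1. They do not: six state no duration and can be read under a Section 7.1 cap, and the other Grade 3 row only permits restart.

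**Conclusion.** The conflict is real, and the text as written is wrong rather than merely incomplete: ten rows provide for resumption at a reduced dose where Section 7.1 orders a permanent stop, most plainly the two AST/ALT rows. Its reach is narrow. It concerns holds with more than 14 days in Cycle 1, starting by Day 7 if only Days 1-21 count. The documents give no expected number of such participants.

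It affects who is re-dosed and the descriptive count of discontinuations due to an AE. A reader might infer that dose finding is compromised. The documents do not support that: a treatment-related hold of this length is a DLT under criterion 9 whether or not the participant later resumes, so DLT counts, mTPI decisions and MTD selection are unchanged. Nor is Section 5.6 flatly contradicted by the 25% limb. Its permission to continue is general and Section 7.1 could limit it; the two overlap without a cross-reference.

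Severity: minor. The conclusion assumes a fixed 21-day cycle calendar and that consecutive days include scheduled off-days.

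**What to change.** 1. Add to Section 6.6.4.1 and Table 7: *In Cycle 1, the 14-day limit in Section 7.1 overrides any longer or unstated Table 7 resume window; the full Table 7 windows apply from Cycle 2.* State whether days after Day 21 of a hold that began in Cycle 1 count toward the limit.
2. In Section 7.1, tie the 25% limb to Cycle 1 as in DLT criterion 9: more than 6 of 24 scheduled doses of MK-8353 and/or selumetinib missed because of drug-related AEs. Cross-refer to Section 5.6 with its condition intact, so that continuation is possible only if the participant is deriving clinical benefit and after Sponsor-investigator discussion. State that this exception does not apply to the 14-day limb. The 14-day limit then has its own role as the hard stop.

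Sample size, dose levels, DLT definition and mTPI rules stay as they are, but the change is more than wording. A few participants with slowly resolving Cycle 1 toxicity who could resume under Table 7 must stop. Any drug-related Cycle 1 hold that covers a full dosing block, as short as 4 days, needs Sponsor discussion to continue. Because the first on-study scan is at 9 weeks (Section 8.2.1.2), benefit would normally have to be judged clinically at that point.

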## 7.2 Participant Withdrawal From the Study

A participant must be withdrawn from the study if the participant or participant's legally acceptable representative withdraws consent from the study.

If a participant withdraws from the study, they will no longer receive study treatment or be followed at scheduled protocol visits.

Specific details regarding procedures to be performed at the time of withdrawal from the study, as well as specific details regarding withdrawal from future biomedical research, are outlined in Section 8.1.9. The procedures to be performed should a participant repeatedly fail to return for scheduled visits and/or if the study site is unable to contact the participant are outlined in Section 7.3.

## 7.3 Lost to Follow-up

If a participant fails to return to the clinic for a required study visit and/or if the site is unable to contact the participant, the following procedures are to be performed:

- The site must attempt to contact the participant and reschedule the missed visit. If the participant is contacted, the participant should be counseled on the importance of maintaining the protocol-specified visit schedule.
- The investigator or designee must make every effort to regain contact with the participant at each missed visit (eg, telephone calls and/or a certified letter to the participant's last known mailing address or locally equivalent methods). These contact attempts should be documented in the participant's medical record.
- Note: A participant is not considered lost to follow-up until the last scheduled visit for the individual participant. The missing data for the participant will be managed via the prespecified statistical data handling and analysis guidelines.

## 8 STUDY ASSESSMENTS AND PROCEDURES

- Study procedures and their timing are summarized in the SoA.
- Adherence to the study design requirements, including those specified in the SoA, is essential and required for study conduct.
- The investigator is responsible for ensuring that procedures are conducted by appropriately qualified or trained staff. Delegation of study site personnel responsibilities will be documented in the Investigator Trial File Binder (or equivalent).
- All study-related medical (or dental) decisions must be made by an investigator who is a qualified physician (or dentist when appropriate).
- All screening evaluations must be completed and reviewed to confirm that potential participants meet all eligibility criteria. The investigator will maintain a screening log to record details of all participants screened and to confirm eligibility or record reasons for screening failure, as applicable.
- Procedures conducted as part of the participant's routine clinical management (eg, blood count) and obtained before signing of ICF may be utilized for screening or baseline purposes provided the procedure met the protocol-specified criteria and were performed within the time frame defined in the SoA.
- Additional evaluations/testing may be deemed necessary by the investigator and or the Sponsor for reasons related to participant safety. In some cases, such evaluation/testing may be potentially sensitive in nature (eg, HIV, Hepatitis C), and thus local regulations may require that additional informed consent be obtained from the participant. In these cases, such evaluations/testing will be performed in accordance with those regulations.

The total amount of blood/tissue to be drawn/collected over the course of the trial, including approximate blood/tissue volumes drawn/collected by cycle and by sample type per subject can be found in the Procedures Manual.

Repeat or unscheduled samples may be taken for safety reasons or for technical issues with the samples.

